6.6.1.5. Last Prescribed Dose

For patients on a prophylactic regimen at any time during the study, the last prescribed dose and dosing frequency will be summarized as a cross tabulation of dosing frequency by dose (IU/kg) in which the number and percentage of patients who were last prescribed each combination of dose and dosing frequency (as applicable) will be tabulated. The last prescribed dose will also be summarized for each dosing frequency using descriptive statistics. If no dose (dosing frequency) changes were prescribed, then a patient's starting dose (dosing frequency) will be used. The dose for the twice weekly regimen will be the average of the two doses given. Percentages will be based on the number of patients in each prophylactic regimen (i.e., not on the

number of patients in each dosing frequency category). This analysis will not include the ITI period and last prescribed dose for these cases is that before the commencement of ITI.

6.6.2. Compliance

Dose compliance will be assessed during the efficacy period and will be summarized for the FAS. Except for doses administered in the clinic, study treatment may be administered by a caregiver. Data from the eCRF and EPD will be considered for the analysis of treatment received and patients' compliance with the study protocol.

6.6.2.1. Compliance in the treatment of bleeding episodes

Bleeding episodes are defined in Section 5.1.2.4. All bleeding episodes during the efficacy period for which there is a date and time for both the onset of the bleeding and treatment of the bleeding will be evaluated for compliance. Compliance will first be determined on a per-bleed basis and then on a per-patient basis. That is, compliance for each bleeding episode will be determined and then the overall percentage of bleeding episodes for which treatment was in compliance will be determined for each patient.

The definition of compliance for the treatment of an individual bleeding episode, as specified by the Sponsor, is no more than 8 hours between the onset of the bleed and the initiation of treatment for the bleed. Thus, the compliance rate for the treatment of bleeding episodes will be measured by determining the proportion of injections administered within a maximum of 8 hours of the initial sign of a bleed, as follows:

$$\text{Treatment of bleed compliance rate} = \frac{\text{Number of first injections to treat a bleed taken within 8 hours of the first sign of a bleed}}{\text{Total number of evaluable bleeding episodes}} \times 100$$

The following circumstances result in a bleeding episode being considered not evaluable for the determination of this compliance rate:

- The type of bleed has been classified as Unknown based on the definition of a bleeding episode (>72 hours between consecutive injections) since there is no onset time
- A missing bleed time for a spontaneous or traumatic bleed
- A bleed time that was recorded as being after the time of treatment

Descriptive statistics for compliance to treat a bleeding episode will be presented for the FAS.

6.6.2.2. Compliance of Prophylactic Injections

The compliance rate of each patient to the prescribed prophylactic and ITI dosing regimens during the efficacy period will be calculated in 2 ways: As dose compliance and as dosing interval compliance. Compliance will first be determined on a per-injection basis and then on a per-patient basis. That is, compliance for an individual dose or dosing interval will be determined and then the overall percentage of doses and dosing intervals that were in compliance will be determined for each patient.

For the purpose of evaluating compliance, the following will be considered per injection:

- The nominal dose taken compared to the nominal dose prescribed
- The actual day of treatment compared to the prescribed day of treatment

An individual dose will be considered compliant if it is within 80%-125% of the prescribed dose. An individual dosing interval will be considered compliant if the time between two prophylactic doses is within 24 hours of the prescribed dosing interval. Prescribed dose and dosing intervals are according to the Investigator. Instructions provided to the patient by the Investigator regarding dose or dosing interval changes will be used to determine compliance as of the date the information was provided to the patient.

The actual dosing intervals will be calculated as the length of time between consecutive prophylactic doses (date/time of PR_{x+1} – date/time of PR_x), PR_{x+1} and PR_x. The actual time between doses will be determined in minutes and converted to days as the number of minutes divided by 1440. The prescribed dosing interval will be taken from the eCRF as recorded by the Investigator. The absolute value of the difference between the actual and prescribed dosing intervals must be ≤1 day (+/- 24 hours) in order to be compliant, or +/- 12 hours for ITI regimens, as these are daily dosing or more frequent.

All prophylactic injections will be used to determine prophylactic dose compliance; only the prophylactic injections used to determine the average prophylactic dosing interval (i.e., intervals not separated by a bleeding episode or surgical/rehabilitation period), as detailed in Section 5.4, will be used to evaluate prophylactic interval compliance. Dose and dosing interval compliance rates per patient will be determined as follows:

$$\text{Dose compliance rate} = \frac{\text{Number of doses taken within 80\%-125\% of prescribed dose}}{\text{Total number of doses}} \times 100$$

where the percentage of a prescribed dose is calculated as: (nominal dose taken/prescribed dose) ×100

and the "nominal dose taken" will be determined from the nominal potency labeled on the vials used by the patient for each injection of rFVIIIIFc.

$$\text{Dose interval compliance rate} = \frac{\text{Number of doses taken within +/- 24 hours (+/- 12 hours for ITI regimens) of prescribed day/time}}{\text{Total number of intervals}} \times 100$$

A patient is considered 'dose compliant' or 'dosing interval compliant' if his respective rate is at least 80%.

Descriptive statistics of the percentage of nominal doses taken per patient $\geq 80\%$ range for dosing compliance as well as frequencies for the dose compliance rate ($< 80\%$, $\geq 80\%$) will be presented for the FAS. Similarly, descriptive statistics of the percentage of doses taken per patient within ± 24 hours (± 12 hours for ITI) of the prescribed day as well as frequencies of the dosing interval compliance rate ($< 80\%$, $\geq 80\%$) will be presented for the FAS.

Based on their per-patient compliance rates for dose and dosing interval (each $< 80\%$, $\geq 80\%$), patients will be further classified into the following mutually exclusive categories for overall compliance to their prophylactic treatment as:

- Both dose and interval compliant
- Dose compliant or interval compliant (but not both)
- Neither dose nor interval compliant

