5.4.2.2. Adjustments Due to Large Injection Intervals

For analysis purposes, the efficacy period will also be adjusted to account for large intervals between injections resulting from missing data. A large interval is defined as >28 days between any 2 adjacent rFVIIIFc injections within a prophylactic treatment regimen and any such intervals will be removed from the efficacy period. The efficacy period prior to each such interval will end at the time of the first injection of this interval and restart (or start if it is the first interval of a treatment regimen) at the time of the second injection of this interval. The efficacy period will be adjusted for each identified interval that is not within a surgical/rehabilitation period. This algorithm applies only to prophylactic regimens and no adjustment for large injection intervals will be made for episodic treatment regimens.

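### SAP 6.6.2.2 measures prophylaxis and ITI compliance without counting the doses due, so a child who misses most doses can be labelled compliant on both dose and interval

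*SAP*

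**What the plan says.** SAP 6.6.2.2 builds two per-patient rates. "Compliance will first be determined on a per-injection basis and then on a per-patient basis".

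- **Dose rate.** "An individual dose will be considered compliant if it is within 80%-125% of the prescribed dose". The denominator is "Total number of doses", and "All prophylactic injections will be used to determine prophylactic dose compliance".
- **Interval rate.** "The actual dosing intervals will be calculated as the length of time between consecutive prophylactic doses". An interval passes if it is within 24 hours of the prescribed interval (12 hours for ITI). The denominator is the number of intervals. Only "intervals not separated by a bleeding episode or surgical/rehabilitation period" are used.
- **Cut-off.** "A patient is considered 'dose compliant' or 'dosing interval compliant' if his respective rate is at least 80" per cent. The two results are then combined into three categories: compliant on both, on one, or on neither.

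SAP 5.4.2.2 adds that when two adjacent injections on prophylaxis are more than 28 days apart, "any such intervals will be removed from the efficacy period". That rule applies to prophylaxis only and is said to address missing data.

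**The concern.** The section is presented as a check of what was taken against what was prescribed. Yet a dose that was prescribed and not taken enters neither the numerator nor the denominator of the dose rate. In the interval rate, one missed dose and eight consecutive missed doses each produce one failing interval. A prophylaxis gap over 28 days, or one split by a bleed, produces no failing interval.

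The result does not move consistently with adherence: a 27-day gap lowers the interval rate, while a 30-day gap does not. Readers will use the compliance tables to judge whether the bleeding and ITI results were obtained on the prescribed regimen. The top category could mislead them for a child whose lapses come in runs.

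**Working it through.** The documents give no figure for the share of due doses taken, so there is nothing to reproduce. I applied the rules to constructed dosing records.

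**Inputs from the documents**
- Cut-off of 80% for each rate; tolerance 24 h, or 12 h for ITI (SAP 6.6.2.2).
- Prophylaxis gaps over 28 days dropped (SAP 5.4.2.2).
- Prescribed prophylaxis interval 3 to 5 days (SAP 3.1.5.2); ITI daily (SAP 3.1.5.3).
- Longest ITI interruption 2 weeks (Protocol 10.2.7.3), used as the ITI gap.

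**Formulas**
- Dose rate = doses taken within 80%-125% / doses taken.
- Interval rate = intervals within tolerance / intervals observed.
- Share of due doses taken per cycle = 5 / [(4 × prescribed interval + gap) / prescribed interval].

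**Boundary pattern: four on-time intervals, then one long gap, repeated, all doses full size.** The dose rate is 100% and the interval rate is 4/5 = 80%, so both pass.

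| Regimen | Gap | Doses due per cycle | Share taken |
|---|---|---|---|
| every 3 days | 27 days | (12 + 27)/3 = 13 | 5/13 = 38.5% |
| every 4 days | 28 days | (16 + 28)/4 = 11 | 5/11 = 45.5% |
| every 5 days | 25 days | (20 + 25)/5 = 9 | 5/9 = 55.6% |
| daily ITI | 14 days | (4 + 14)/1 = 18 | 5/18 = 27.8% |

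Counted as a full record over 390 days, the first row is 51 of 131 due doses (38.9%).

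**Gaps over 28 days.** On a 3-day regimen with 30-day gaps after every four on-time intervals, 51 of 141 due doses are taken (36.2%) and the interval rate is 100%, because the gaps are removed. Alternating 3-day and 30-day intervals gives 51 of 276 (18.5%), with both rates 100%.

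**Less extreme patterns (assumed).** I simulated 60 prescribed doses every 3 days, with misses occurring in runs and all other doses on time and full size. The entries are the chance of being classed compliant on both.

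| Doses missed | Independent misses | Mean run 3 | Mean run 4 | Mean run 5 |
|---|---|---|---|---|
| 30% | 8% | 88% | 97% | 99% |
| 40% | under 1% | about 46% | about 80% | 93% |
| 50% | 0% | 7% | about 40% | 70% |

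If 10% of the otherwise on-time intervals are also more than 24 h off, the 40% row for runs of 3, 4 and 5 falls to about 13%, 34% and 56%. The documents give no run lengths or lateness rate. The rule detects isolated misses well and runs of misses poorly.

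**The case against.** The strongest reply is that these tables are not the only account of treatment delivered. SAP 6.6.1.3 reports each patient's average weekly dose (daily for ITI) and average dosing interval, and SAP 6.6.1.4 and 7.4.7 report annualized consumption. Both main examples would show there. The 3-day child has an average interval of 39/5 = 7.8 days against 3 prescribed, and the ITI child averages 200 × 5/18 = 56 IU/kg/day against 200. This stands, with one limit: those measures use the efficacy period, so gaps over 28 days drop out of them too, and none of them corrects the label.

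The 38% figure is a boundary case. One further late interval takes the child below 80%. It should not be read as typical, or as a floor.

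A reader might infer that the 28-day rule hides lapses. The documents do not support that: SAP 5.4.2.2 attributes such gaps to missing data, and the same days leave the ABR denominator. Whether a given gap is a lapse or an absent record is unknown.

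The interval numerator mentions the prescribed day or time, which could suggest a calendar schedule. But the text defines the test as actual against prescribed interval, and the denominator is observed intervals. Doses not taken are uncounted on either reading.

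Finally, a crude doses-due denominator would be unfair. Half-life assessment during ITI requires at least 72 hours of washout and 72 hours of sampling without further doses (Protocol 10.2.7.1), and the Investigator may suspend treatment before ITI (Protocol 10.2.7). This is right, and the fix allows for it.

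**Conclusion.** The point holds as a labelling fault. By the wording of SAP 6.6.2.2, a child can take 38% (3-day regimen), about 45% (4-day), 56% (5-day) or 28% (daily ITI) of due doses and still be classed compliant on both dose and interval. These shares rest on the constructed pattern of one long gap in every five intervals with all else on time. How often real children come near it cannot be told from the documents.

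A reader might infer that the ABR, the inhibitor incidence or the ITI response is distorted. The documents do not support this. The prophylaxis compliance category defines no analysis set and no ABR subgroup, enters neither the primary endpoint nor the ITI response definitions, and sits in a study without hypothesis tests. What is at stake is whether a reader is misled about adherence. It is worth correcting because the correction is cheap.

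**What to change.** In SAP 6.6.2.2:

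1. Add a per-patient rate: doses taken within 80%-125% of prescribed / doses due, where doses due = time on regimen / prescribed interval from the eCRF.
2. Exclude from time on regimen the surgical/rehabilitation periods, the protocol-required ITI washout and PK sampling windows, and documented Investigator-directed suspensions.
3. Count a bleed-treatment injection given on a due day, or within the tolerance of one, as that dose.
4. Base the top category on this rate together with the interval rate. Label the present dose rate *among doses taken*.
5. Report the new rate with gaps over 28 days excluded, consistent with SAP 5.4.2.2, and again with them included as a sensitivity row.

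In the 3-day example the rate used for classification falls from 100% to 38.5%, and the child leaves the top category. A child whose gaps all exceed 28 days will be visible only in the sensitivity row.

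The cost is SAP wording and derivations from data already collected. The downside is that reported compliance becomes less favourable, and unrecorded injections count as missed unless vial accountability (Protocol 12.1.4) recovers them.

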6.6.2.3. Compliance of EPD Contemporaneous Data Entry

Injections must be entered into the EPD within 7 days from the date of the injection. Injections entered outside the 7-day window will be reported as protocol deviations. Descriptive statistics of the percentage of the patients with fewer than 80% of their total individual EPD records entered within this 7 day window and those with $\geq 80\%$ of records meeting this criteria will be presented for the FAS as well as a summary of % compliance to this criteria by patient.

7. EFFICACY ANALYSIS

7.1. General Efficacy Principles

Efficacy analyses will be based on the Full Analysis Set and unless otherwise specified, presented by the treatment regimen groups described in Section 5.1.1.1.

Additionally, the general efficacy and surgical/rehabilitation periods are defined in Section 5.4. Data on bleeding and rFVIIIFc consumption will be based on the efficacy period; surgical evaluations will be based on the surgical/rehabilitation period.

Analysis of efficacy endpoints that are visit-based will include data from all study visits whether or not in the efficacy period, unless that visit is coincidental with a surgical/rehabilitation period for a major surgery, in which case it would be excluded.

7.2. Multiplicity

Multiplicity is not a concern in this study since no statistical tests are being performed on the efficacy endpoints.

7.3. Analysis of Primary Endpoint(s)

All efficacy endpoints are secondary. Therefore, there will be no analysis of a primary efficacy endpoint.

7.4. Analysis of Secondary Endpoints

7.4.1. Bleeding Episodes

Bleeding episodes will be recorded in both the EPD and eCRF; this information will be used to derive the secondary efficacy endpoints. During the course of the study the Investigator is given the opportunity to disagree with the type of bleeding (spontaneous, traumatic) as classified by the patient/caregiver, and the patient/caregiver is subsequently given the opportunity to agree or disagree with the reclassification. If the patient/caregiver agrees with the Investigator's assessment, then all analyses subset by type of bleeding will be based on the Investigator's determination of the bleeding type whether or not the change was made to the patient's records.

Standardized definitions of bleeding episodes are provided in 5.1.2.4

Bleeding episodes of an unknown type will be included in the determination of the annualized bleeding rate and in summaries based on bleeding episodes but, unless specified otherwise, will not be included in summary tables where endpoints are summarized by type of bleed.

7.4.2. Summary of Bleeding Episodes

As a description of the raw data collected in this study, the unadjusted number of bleeding episodes per patient will be summarized using descriptive and categorical (e.g. 0, >0-5, >5-10,

>10-15, etc.) statistics over all bleeding episodes. Of note, the number of patients with a bleeding episode for which the location is unknown will be tabulated in these summaries but no further analysis of unknown bleeding locations is planned.

The total patient years followed during the efficacy period (summed over all patients overall) will be provided in order to put the unadjusted numbers in perspective.

These summaries will be further broken down by bleed type and location. These tables will be presented by treatment regimen and for the inhibitor subgroups, as described in Sections 5.1.1.1 and 5.1.1.2 respectively.

7.4.3. Annualized Number of Bleeding Episodes per Patient (ABR)

The per-patient annualized number of bleeding episodes, hereafter referred to as the annualized bleeding rate (ABR), will be calculated for each patient using the following formula:

$$\text{ABR} = \frac{\text{Number of bleeding episodes during the efficacy period}}{\text{Total number of days during the efficacy period}} \times 365.25$$

The ABR will be summarized using descriptive and categorical (e.g. 0, >0-5, >5-10, >10-15, etc.) statistics for the FAS. All types of bleeding episodes (spontaneous, traumatic, and type unknown) will be included in determining the annualized number.

These tables will be presented by treatment regimen and for the inhibitor subgroups, as described in Sections 5.1.1.1 and 5.1.1.2 respectively.

This analysis will also be presented by the following subgroups:

- History of bleeding (estimated frequency of bleeds in prior 3 months: 0, 1-2, 3-5 and >5)
- Patients with no major protocol deviations potentially impacting efficacy (see Section 6.5)

7.4.4. Annualized Number of Bleeding Episodes per Patient by Type and Location of Bleed

For completeness, summaries of the ABR will also be provided for the following subsets of bleeds for the FAS:

- Type of bleeding (spontaneous, traumatic, unknown)
- Location of bleeding (joint, muscle, internal, skin/mucosa)
For the purpose of analysis bleeding episodes with a location of iliopsoas will be treated as a muscle bleed; however, the location will be displayed as iliopsoas in the listings.
- Location and type of bleeding (joint spontaneous, joint traumatic, muscle spontaneous, muscle traumatic, internal spontaneous, internal traumatic, skin/mucosa spontaneous, skin/mucosa traumatic)

These tables will be presented by treatment regimen and for the inhibitor subgroups, as described in Sections 5.1.1.1 and 5.1.1.2 respectively.

7.4.5. Assessment of Response to Treatment with rFVIII Fc for Bleeding Episodes Using the 4-Point Bleeding Response Scale

Using the EPD, each patient's parent/caregiver rates the treatment response to any bleeding episode using a 4-point scale. Ratings of treatment response are made approximately 8 to 12 hours from the time the injection is given to treat the bleeding episode and prior to any additional doses of rFVIII Fc given for the same bleeding episode. Response is also assessed by the Investigator and recorded on the eCRF for those patients who are treated in the hospital with rFVIII Fc for major bleeding episodes.

The 4-point scale is as follows:

- Excellent
- Good
- Moderate
- None

Response categories of excellent and good will be presented combined as well as individually. The number and percentage of injections in each response category will be tabulated based on all injections. Two summaries will be provided. In the first summary percentages will be based on the total number of injections administered for bleeding episodes for which a response was provided. In the second summary percentages will be based on the total number of bleeding episodes whether or not a response was provided.

The assessment of response will also be summarized on a per patient basis by presenting the number and percentage of first injections to treat a bleeding episode for which the response to the treatment was categorized as excellent, good, moderate, or no response, using both approaches to determine the percentages.

The patient's assessment of response will be summarized for the FAS. In order to evaluate if there is a relationship between compliance to treat a bleed and response to the treatment of the bleed, this endpoint will additionally be summarized by compliance to treat the bleed where compliance will be based on the individual bleeding episodes.

These data will be provided in a listing which will include the total number of bleeding episodes and the number of first injections for which a response assessment was provided.

7.4.6. Total Number of EDs per Patient

The total number of EDs on rFVIII Fc for each patient will be summarized. This analysis is described in Section [6.6.1.1](#).

7.4.7. Total Annualized rFVIIIFc Consumption per Patient for the Prevention and Treatment of Bleeding Episodes

Total annualized rFVIIIFc consumption per patient for the prevention and treatment of bleeding episodes will be summarized for the FAS using descriptive statistics. See Section 6.6.1.4 for details on the annualized rFVIIIFc consumption derivation.

These tables will be presented by treatment regimen and for the inhibitor subgroups, as described in Sections 5.1.1.1 and 5.1.1.2 respectively.

7.4.8. Number of Injections and Dose per Injection of rFVIIIFc Required to Resolve a Bleeding Episode

The number of injections and average dose per injection (IU/kg) required to resolve a bleeding episode will be determined on both a per-bleeding episode and per-patient basis. For completeness, the total dose (IU/kg) administered to resolve a bleeding episode will also be determined on both a per-bleeding episode and per-patient basis. See Section 7.4.1 for details on the definition of a bleeding episode. A bleeding episode is considered resolved when treatment for the bleeding is no longer needed.

Per bleeding episode: The total number of injections will include the initial injection for a spontaneous bleed (SB), a traumatic bleed (TB), or a bleed of unknown type plus all injections identified as follow-up (FU) treatment for that bleed. For each bleed, the average dose per injection will be calculated as the average of all doses (IU/kg) administered among the SB/TB/Unknown and FU injections administered to treat that bleed; the total dose will be the sum of these doses. The number of injections required for the resolution of a bleeding episode will be summarized across all bleeding episodes both categorically (1, 2, 3, 4, >4; 1, >1; and ≤2, >2) and with descriptive statistics. The average dose per injection and total dose required for resolution of a bleeding episode will be summarized using descriptive statistics.

Per patient: The number of injections, average dose per injection, and total dose required to resolve each bleeding episode, as determined for the per-bleeding episode summaries, will be averaged across all bleeding episodes for each patient. The average number of injections required for resolution of a bleeding episode will be summarized both categorically (1 to <2, 2 to <3, 3 to <4, and ≥4; and 1 to <2, ≥2) and with descriptive statistics. The averages for the per-patient average dose per injection and total dose required for resolution of a bleeding episode will be summarized using descriptive statistics.

Bleeding episodes that were treated with non-study medication will be included in the determination of the number of injections required to resolve the bleeding episode but not in either the average dose per injection or total dose required.

For the above analysis, data from the FAS will be summarized. These tables will be presented by treatment regimen and for the inhibitor subgroups, as described in Sections 5.1.1.1 and 5.1.1.2 respectively.

